Study Duration:	
 
 First subject enrolled:	June, 2015	
 
 Last subject enrolled:	October, 2016	
 
 Last subject completes Month 12 Visit:	December, 2017	
 
 Last subject completes Month 24 Visit:	December, 2018	
 
 Long-term surveillance completed (Month 36):	December, 2019	
 
	First subject enrolled:	June, 2015	Last subject enrolled:	October, 2016	Last subject completes Month 12 Visit:	December, 2017	Last subject completes Month 24 Visit:	December, 2018	Long-term surveillance completed (Month 36):	December, 2019
First subject enrolled:	June, 2015										
Last subject enrolled:	October, 2016										
Last subject completes Month 12 Visit:	December, 2017										
Last subject completes Month 24 Visit:	December, 2018										
Long-term surveillance completed (Month 36):	December, 2019										

Primary Outcome Measures:
	
Primary safety endpoint: A composite of major adverse events (MAE) comprising death, any major amputation performed on the target limb or clinically-driven target lesion revascularization (TLR) through 30 days.
 
Primary effectiveness endpoint: Primary stent patency rate at 12 months. Patency is defined as no significant reduction in luminal diameter (i.e. < 50% diameter stenosis) since the index procedure. Luminal diameter is assessed by core lab using angiography or duplex ultrasound imaging. Loss of primary stent patency is deemed when peak systolic velocity ratio (PSVR) is >2.0, or where angiography reveals >50% diameter stenosis, or where the subject undergoes clinically-driven TLR. When both imaging modalities are available, angiography takes precedence.
 

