## 4. INTRODUCTION

The purpose of this statistical analysis plan is to provide additional details on the derivation of variables and statistical analyses to be performed for this study. The database will lock when the 12-month visit is completed for all patients. All planned analyses will be performed at this time. There will continue to be annual follow-up visits for the collection of relevant medications and adverse events for 2 additional years. Interim analyses will be conducted for annual progress reporting as described herein.

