### 9.2.3. Handling of Dropouts or Missing Data

For all primary, secondary and exploratory analyses, no imputation of missing data is planned. Subjects who have ascertainment of status at a later out-of-window date (for example, subjects who are known to be free of MAE past 30 days but missed the 30 day visit) are not considered missing as their status is known and their data will be used as noted previously. A sensitivity analysis, specifically a tipping point analysis, will be used to assess the impact of missing data on the study conclusions for the primary endpoints. This sensitivity analysis will be performed on the ITT analysis set.

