### 9.2.4. Interim Analyses and Data Monitoring

There is no interim analysis planned with the purpose of altering the Protocol or planned statistical analyses. When all data have been collected and imaging completed for the co-primary endpoints (through 12 months), the database will be cleaned and the primary study analysis conducted. All data available at that time will be summarized for reporting and regulatory filing purposes (PMA submission on primary data set). Additional analyses will be conducted for annual reporting purposes and when all data have been collected for the 24 and 36 month visits.

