#### 9.2.8. Analysis Windows and Definitions

Study subjects are required to return for clinic visits post-procedure at Day 30 ( $\pm 7$  days), Month 12 (365 days  $\pm 30$  days), and Month 24 (730 days  $\pm 60$  days). A final study visit at Month 36 (1095 days  $\pm 60$  days) is required as well; however, this visit may be completed either as a clinic visit or telephone visit. For ascertainment of the primary endpoints, if the subject is known to be event free at at least the lower limit of the visit window, that subject will be considered event free for the analysis. Thus, if a subject misses the 30 day visit, but is determined to have been event free up to the 12 month visit, then that subject will be considered event free. If the subject has no data past the lower boundary of the visit window, their data will be considered missing.

For the purposes of these analyses, 12 months is defined as 365 days post procedure, and similarly 24 and 36 months are defined as 730 and 1095 days, respectively. Procedure is considered day 0 so that days from procedure is defined as (visit date – procedure date).

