#### 9.4.2. Primary effectiveness endpoint:

The primary outcome measure for effectiveness is primary stent patency rate at 12 months as defined in Section 6.2.2. The one-sided lower 97.5% Agresti-Coull confidence bound will be computed for patency and this lower bound will be compared to the effectiveness performance goal of 66% for bare Nitinol stenting as defined by the VIVA Physicians, Inc.[4]. The performance goal will be met if the lower bound is greater than 66%. The mITT analysis population will be used for this endpoint; however, only subjects with valid endpoint data without imputation will be included. This includes all subjects with imaging data qualifying as a 12 month visit and/or subjects without imaging data who experienced a CDTLR through 12 months (365 days). Additionally, if a subject is missing stent patency status at the 12 month visit window but is found to be patent at a later out-of-window date, the subject will be considered patent at 12 months. Sensitivity analyses for excluding missing data will be conducted as described in Section 9.2.3 above.

Both primary endpoints must be met in order to declare trial success.

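### A late patent image can fill a missing 12-month patency status with no latest date and no counterpart for a late non-patent image, so entry to the primary analysis depends on the result and on enrollment date

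*SAP*

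**What the plan says.** SAP section 9.4.2 limits the primary effectiveness analysis to mITT subjects with valid endpoint data. It describes them thus: "This includes all subjects with imaging data qualifying as a 12 month visit and/or subjects without imaging data who experienced a CDTLR through 12 months", the CDTLR limit being day 365. It then adds a route for a subject without status in the 12-month window: one who "is found to be patent at a later out-of-window date, the subject will be considered patent at 12 months". The section gives no latest day for that image. It gives no parallel sentence for a late image that shows loss of patency.

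No other section supplies a limit:

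- Section 9.2.3 says that subjects whose status is established later "are not considered missing as their status is known and their data will be used as noted previously".
- Section 9.2.8 fixes only the early edge: "If the subject has no data past the lower boundary of the visit window, their data will be considered missing".

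Patency is also determined at Month 24 (section 6.2.3), in a window of 730 ± 60 days (section 9.2.8). A Month 24 scan therefore meets the wording of the fill rule.

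On timing, section 4 states: "The database will lock when the 12-month visit is completed for all patients". The synopsis gives "First subject enrolled: June, 2015", last enrollment in October 2016, and December 2017 against "Last subject completes Month 12 Visit". Section 9.2.4 adds: "Additional analyses will be conducted for annual reporting purposes and when all data have been collected for the 24 and 36 month visits".

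**The concern.** The rule brings a subject into the numerator and denominator because a late image was favourable. A subject with the same missing 12-month image and an unfavourable late image has no stated place, and on the wording stays missing. Selecting on the result in this way raises the estimated patency rate.

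The open date enlarges the effect. At a single calendar lock, early enrollees have had up to about 18 months after the 12-month window in which to produce a favourable image, and the last enrollees two months at most. Two subjects with the same missing image can be classified differently only because of when they enrolled.

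At stake is the test of patency against the 66% performance goal, one of the two tests that decide trial success. The planned safeguard does not reach the problem: the tipping-point analysis in section 9.2.3 addresses missing data, and the same section says that subjects with later status are not missing.

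**Working it through.** **1. The plan's own figure.** Inputs from section 9.1: goal 66%, assumed patency 75%, one-sided 97.5% Agresti-Coull lower limit, 230 evaluable, 85% power. With z = 1.96, ñ = n + z² and p̃ = (x + z²/2)/ñ, the lower limit is p̃ − z·√(p̃(1 − p̃)/ñ).

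- 165/230: ñ = 233.84, p̃ = 0.7138, lower limit 65.6% (fail).
- 166/230: p̃ = 0.7181, lower limit 66.04% (pass).

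The rule is therefore at least 166 of 230. By the exact binomial, the type I error at 66% is 0.027 and the power at 75% is 85.6%. The stated 230 is reproduced.

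**2. Who can have a Month 24 scan by the lock.** Inputs: enrollment June 2015 to October 2016, lock in December 2017 (synopsis, section 4), Month 24 window opening at day 730 − 60 = 670 (section 9.2.8). The days within the months are not given, so ranges are shown.

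- First enrollee at lock: day 885 (30 June 2015 to 1 December 2017) to day 944 (1 June 2015 to 31 December 2017).
- Last enrollee at lock: day 396 (31 October 2016 to 1 December 2017) to day 456 (1 October 2016 to 31 December 2017).
- The 12-month window closes at day 365 + 30 = 395. Time left after it is 1 to 61 days for the last enrollee and up to 944 − 395 = 549 days for the first.

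Assuming uniform enrollment (the SAP gives no curve), the share that has reached day d is (first enrollee's day at lock − d) / (length of enrollment in days).

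| Day reached | Lowest | Highest |
|---|---|---|
| 670 | (885 − 670)/489 = 44% | (944 − 670)/488 = 56% |
| 730 | (885 − 730)/489 = 32% | (944 − 730)/488 = 44% |

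The shape of enrollment matters. In the case of 1 June 2015 to 31 October 2016 with a 31 December 2017 lock, the day-670 share is 274/518 = 53%. It falls to 0.53² = 28% if enrollment rises linearly, and rises to 1 − 0.47² = 78% if it is front-loaded.

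**3. How many can be filled.** Section 9.1 gives 271 enrolled and expects more than 230 evaluable, so at most about 271 − 230 = 41 are missing. In the same case, 30% have passed the end of the Month 24 window (day 790: 154/518) and 53% have passed its opening. That gives 41 × 0.30 ≈ 12 to 41 × 0.53 ≈ 22 subjects. Both are upper estimates, because a subject who has left the study will have no Month 24 scan.

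**4. Effect on the test.** Assumptions: true patency 66%; 230 subjects with observed status; each of 41 missing subjects has a Month 24 scan with probability f (0.30 to 0.53), which is patent with probability q (0.50 to 0.66); non-patent late scans stay missing. The number filled, K, is binomial(41, f·q). The type I error is the average over K of the chance that observed successes plus K reach the Agresti-Coull threshold for n = 230 + K.

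| f | q | Expected fills (41·f·q) | Expected rate | Type I error |
|---|---|---|---|---|
| 0 | – | 0 | 66.0% | 0.027 |
| 0.30 | 0.50 | 6.1 | 66.9% | 0.044 |
| 0.30 | 0.66 | 8.1 | 67.2% | 0.052 |
| 0.53 | 0.50 | 10.9 | 67.5% | 0.068 |
| 0.53 | 0.66 | 14.3 | 68.0% | 0.091 |

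The expected rate is (230 × 0.66 + fills)/(230 + fills).

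**5. What drives it.** Start from 165/230, a fail. Adding four late subjects, all patent, gives 169/234 with a lower limit of 66.1%, a pass. If one of the four is non-patent and is counted, the result is 168/234 with a lower limit of 65.7%, still a fail. The change of result comes from the one-way entry. The open date sets how many subjects can enter that way.

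**The case against.** **A later patent image is good evidence of patency at 12 months.** For the individual subject that is right, and section 9.2.3 gives it as the rationale. It does not answer the point about entry: the same search for late images, when it returns an unfavourable one, has no stated consequence.

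**The open date by itself is not the main bias.** This stands. Ascertainment that depends on enrollment date distorts the rate only if enrollment date is related to patency, which nothing in the SAP suggests, or if the fill is one-way. The fill as written is one-way.

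**A reader might infer that about half the cohort can be filled.** The SAP does not support that. The 44% to 56% is calendar opportunity under assumed uniform enrollment. Only subjects with missing status can be filled, and since section 9.1 counts drop-out among the reasons for non-evaluability, some of them will have no later scan.

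**A reader might infer that the primary result will be recalculated at the 24- and 36-month analyses.** The SAP does not plan this. Sections 4 and 9.2.4 place the primary analysis at the 12-month lock, and the later analyses serve annual reporting and the later visits. What remains is that no sentence rules out re-deriving 12-month patency then.

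**A reader might infer distorted site, US/OUS or Japan comparisons.** That would need regions or sites to have started at different times. The SAP gives no such dates, and section 9.2.7 calls its subgroup analyses exploratory.

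**A cap discards information.** On the planned dates, a day that everyone can reach is no later than about day 396 to 456, and at the low end this nearly removes the fill. That is a real cost, which is why the uncapped result should still be reported.

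**Conclusion.** The concern holds in a limited form. Section 9.4.2 admits subjects with missing 12-month status on a favourable late image, without a latest date and without a counterpart for an unfavourable one. On the plan's own dates, the opportunity runs from at most about 60 days past the window for the last enrollees to about 18 months for the first. With 12 to 22 late scans among 41 missing subjects, the one-sided type I error is about 0.04 to 0.09 instead of 0.027.

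That range rests on four assumptions: roughly uniform enrollment, a lock in December 2017, 50% to 66% of late scans patent, and non-patent late scans left missing. It shrinks if more than 230 subjects are evaluable or if the missing subjects are mostly dropouts. It grows if enrollment was front-loaded or if cleaning delays the lock. The cause is the one-way fill; the missing date limit enlarges it and ties it to enrollment date. No planned sensitivity analysis removes the fill.

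**What to change.** Amend section 9.4.2 as follows, and align sections 9.2.3 and 9.2.8:

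- Accept a late image only up to one fixed post-procedure day, the same for all subjects, that the last enrollee can reach before the 12-month lock.
- State that scans in the Month 24 window do not determine 12-month status.
- Apply the same cut-off to late non-patent images and state how they are counted, so that entry to the analysis does not depend on the result.
- Report the primary test with no late fill, and with uncapped fill, as two sensitivity rows.
- State that the 12-month patency dataset is not re-derived after the lock.

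The cost is SAP wording, one cut-off in the derivation and two table rows. No new data are needed. A few early enrollees move from evaluable to missing, which slightly lowers precision and places them within the tipping-point analysis.

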### 6.2.2. Primary Effectiveness Endpoint

The primary outcome measure for effectiveness in the MIMICS-2 Study is primary stent patency rate at 12 months.

Patency is defined as no significant reduction in luminal diameter (i.e., < 50% diameter stenosis) since the index procedure. Luminal diameter is the value determined by the independent core lab. Loss of primary stent patency is deemed when PSVR >2.0, or where angiography reveals >50% diameter stenosis, or where the subject undergoes CDTLR. When both imaging modalities are available, angiography takes precedence.

[REDACTED]

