### *Final sample size determination*

In order to statistically power both of the primary endpoints simultaneously, 230 evaluable subjects at 12 months are required. It was initially determined that in order to allow for attrition, a sample size of 280 subjects should be enrolled in the MIMICS-2 Study; however, enrollment was stopped at 271 subjects with the expectation that greater than 230 subjects will be evaluable at 12 months based on current drop-out rates and updated estimates of availability of diagnostic DUS images. The power for the primary safety endpoint is actually >99%, keeping the overall study power at approximately 85%.

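### Section 9.4.2 admits late-only scans to the primary patency analysis when they are patent but gives no entry when they show loss, so the outcome decides who is counted

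*SAP*

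**What the plan says.** Section 9.4.2 restricts the primary effectiveness analysis to mITT subjects with valid, non-imputed endpoint data. It describes that group as "subjects with imaging data qualifying as a 12 month visit and/or subjects without imaging data who experienced a CDTLR through 12 months (365 days"). It then adds one late route: a subject with no patency status in the window who is "found to be patent at a later out-of-window date, the subject will be considered patent at 12 months". A late scan showing loss is not mentioned.

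Three other places bear on this:

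- Section 9.2.8 sets the Month 12 window at 365 ± 30 days. Its carry-back rule covers only the subject "known to be event free at at least the lower limit of the visit window, that subject will be considered event free".
- Section 9.2.3 says that subjects with later ascertainment "are not considered missing as their status is known and their data will be used as noted previously". Nothing earlier, or later, says how a late loss is to be used.
- Section 6.2.2 defines the endpoint without reference to the window: "Loss of primary stent patency is deemed when PSVR >2.0, or where angiography reveals >50% diameter stenosis, or where the subject undergoes CDTLR".

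Section 9.1 shows that missing images were a live issue. Enrollment stopped at 271, with more than 230 expected to be evaluable, "based on current drop-out rates and updated estimates of availability of diagnostic DUS images".

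**The concern.** Take two subjects with no in-window scan and no revascularization by day 365, each scanned after the window. If the scan is patent, the subject adds one to both numerator and denominator. If it shows loss, the subject fits none of the categories in section 9.4.2 and adds to neither. Entry by this route therefore depends on the outcome, which pushes observed patency upward and can raise the false-success probability above the stated one-sided 2.5%.

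The safety analysis in section 9.4.1 has a similar late rule, but there it does no harm: death, amputation and revascularization carry dates, so an event after day 30 still leaves 30-day status known. Restenosis found on imaging has no onset date.

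A smaller gap points the same way. A core-lab imaging loss before day 335 (365 − 30), with no revascularization and no window scan, is a loss under section 6.2.2 but is not among the groups listed in section 9.4.2. It should be rare, because the SAP schedules no visit between Day 30 and Month 12.

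**Working it through.** **Inputs from the SAP (section 9.1).** Goal 66%; one-sided lower 97.5% Agresti-Coull limit; assumed patency 75%; 230 evaluable; 85% power; 271 enrolled, which leaves 271 − 230 = 41 subjects without in-window status if exactly 230 have it.

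**Assumed, not in the SAP.** M late-only subjects (5, 10 or 20) in addition to 230 in-window subjects; late patency q of 66% or 60%; F subjects who enter as failures through revascularization without imaging.

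**1. The plan's own figure.** With z = 1.96 and p̃ = (x + z²/2)/(n + z²), the limit is p̃ − z·√[p̃(1 − p̃)/(n + z²)].

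- n = 230: x = 165 gives 65.59% (fail); x = 166 gives 66.04% (pass).
- Power: P(X ≥ 166 | 0.75) = 85.6%, so the planned 230 reproduces.
- False success: P(X ≥ 166 | 0.66) = 2.7%, slightly above 2.5% because counts are discrete.

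**2. The written rule.** If k of the M late scans are patent, the denominator is 230 + k. Let c(n) be the smallest passing count at n. Then

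P(false success) = Σₖ Bin(k; M, q) × P[Bin(230, 0.66) ≥ c(230 + k) − k].

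If both results are used, the denominator is 230 + M whatever k is. If late scans are not used, it stays at 230.

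| Late-only subjects M | Written rule, q = 66% | Written rule, q = 60% | Both results used, q = 66% | None used |
|---|---|---|---|---|
| 5 | 3.5% | 3.4% | 2.2% | 2.7% |
| 10 | 4.4% | 4.2% | 2.6% | 2.7% |
| 20 | 8.3% | 7.4% | 2.5% | 2.7% |

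Taking the late-only subjects from within the 230 instead of adding them gives 3.3%, 4.6% and 8.5% for the written rule at q = 66%.

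**3. Shift in the estimate (q = 66%).** (230 × 0.66 + 0.66M)/(230 + 0.66M) − 0.66 = 0.5, 0.9 and 1.8 percentage points for M = 5, 10 and 20.

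**4. The opposite route.** Subjects without imaging who had a clinically driven revascularization enter only as failures. Adding F of them (q = 66%):

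| M | F = 0 | F = 1 | F = 2 | F = 3 | F = 5 |
|---|---|---|---|---|---|
| 5 | 3.5% | 2.65% | 2.0% | – | – |
| 10 | 4.4% | 3.6% | 2.9% | 2.3% | – |
| 20 | 8.3% | – | – | 4.6% | 2.9% |

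**5. A case where the rule decides the result.** In window, 164/230 has a limit of 65.1% and fails. Add ten late-only scans, 7 patent and 3 lost:

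- written rule: (164 + 7)/(230 + 7) = 171/237, limit 66.1%, pass;
- both results: 171/240, limit 65.2%, fail.

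**6. Losses before the window.** If an expected 1 or 2 such losses among 230 are left out, the 2.7% becomes 3.0% or 3.6%.

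**7. Plausible size of M.** Enrollment ran from June 2015 to October 2016 and the last Month 12 visit was due in December 2017. At that lock only early enrollees can have a Month 24 scan, so 5 to 10 is likelier than 20.

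**The case against.** The strongest defence is that the asymmetry has a logic. A stent patent after the window, with no reintervention, was patent at 12 months, whereas a late loss does not establish loss at 12 months. Leaving the late loss unknown fits a no-imputation policy, and counting it as failure costs power: with 20 late scans, in-window patency 75% and late patency 65%, power is 80.8% against 85.6% when they are not used. This stands as a reason to regard late losses as uncertain. It does not justify a denominator made up of the late successes alone.

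Second, section 9.4.2 says the set includes certain groups, and section 9.2.3 is neutral about outcome, so late losses might be meant to enter. The text permits that hope, but nowhere says whether such a subject counts as patent, lost or missing. Section 9.4.2 is the specific rule and names only the patent case.

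Third, the net error may be small. With 5 late scans, a single failure without imaging brings 3.5% to 2.65%, just under the baseline, and the 0.8-point rise for 5 scans is about as wide as the ordinary variation from discreteness (2.0% to 2.75% for n from 225 to 271). Both points are correct. But the offset depends on two counts that nobody plans, so it cannot be relied on for error control.

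Fourth, the SAP plans a tipping-point analysis, a Kaplan-Meier figure of primary patency and a listing of patency results. These would help a reader see the issue. None changes the success rule, and the tipping-point analysis does not vary the late patent subjects, who are declared not missing.

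Finally, section 9.4.2 refers to the definition in section 6.2.2, which weakens the point about losses before the window. That gap is minor and needs only a clarifying sentence.

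**Conclusion.** The concern holds. The late route in section 9.4.2 selects on outcome, for the endpoint that sets the trial's size and on which its success depends. Taken alone, it raises false success from 2.7% to about 3.5%–4.4% for 5 to 10 late-only subjects, and to 8.3% for 20. These figures assume 230 in-window subjects, true patency of 66% and late patency of 66%; late patency of 60% changes them little. The net effect after failures without imaging could be nil or even conservative, and the SAP gives no count for either route. The case for correction therefore rests on the form of the rule and on its power to reverse a borderline result, not on a known bias. It should be fixed.

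**What to change.** Write one rule for late-only scans that does not depend on their result, and fix it before the database lock described in section 9.2.4 ("When all data have been collected and imaging completed for the co-primary endpoints (through 12 months), the database will be cleaned"). Either:

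- **A, use none.** Subjects whose only scan falls after the 12-month window are missing for the primary analysis and enter the tipping-point analysis; or
- **B, use both.** Patent with no intervening target lesion revascularization counts as patent; not patent counts as loss.

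Report the option not chosen as a sensitivity analysis. State that a core-lab imaging loss before or within the window counts as a loss, in line with section 6.2.2. Bring sections 9.2.3 and 9.2.8 into agreement. Report the numbers of late-only patent, late-only not patent, and imaging-less revascularization subjects.

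The cost is SAP wording and one derived variable. The estimate may be slightly lower. Option A gives up some informative late patent scans; option B is conservative, because some late losses will have occurred after 12 months.
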